Investigations	22 (25.3%)	Skin and Subcutaneous Tissue Disorders	36 (41.4%)
Alanine Aminotransferase Increased	7 (8.0%)	Hemangioma of skin	32 (36.8%)
Aspartate Aminotransferase Increased	7 (8.0%)	Rash	7 (8.0%)
White Blood Cell Count Decreased	3 (3.4%)	Pruritus	6 (6.9%)
Blood Bilirubin Increased	3 (3.4%)	Rash Maculo-Papular	3 (3.4%)
Electrocardiogram QT prolonged	2 (2.3%)	Flushed skin	1 (1.1%)
Elevated CR-MB	2 (2.3%)	Palmar-plantar erythrodysesthesia syndrome	1 (1.1%)
Troponin increased	1 (1.1%)	Urticaria	1 (1.1%)
White Blood Cell Count Increased	1 (1.1%)		
Neutrophil count decreased	1 (1.1%)	General Disorders and Administration Site Conditions	18 (20.7%)
Blood Thyroid Stimulating Hormone Increased	1 (1.1%)	Pyrexia	9 (10.3%)
Blood prolactin increased	1 (1.1%)	Asthenia	5 (5.7%)
Blood myoglobin increased	1 (1.1%)	Fatigue	4 (4.6%)
Blood creatine phosphokinase increased	1 (1.1%)	Chills	1 (1.1%)
Blood Creatinine Increased	1 (1.1%)		
Hypokalaemia	1 (1.1%)	Endocrine Disorders	9 (10.3%)
		Hypothyroidism	8 (9.2%)
		Hyperthyroidism	1 (1.1%)
		Gastrointestinal Disorders	7 (8.0%)
		Nausea	2 (2.3%)
		Diarrhea	2 (2.3%)
		Abdominal Distension	1 (1.1%)
		Mouth Ulceration	1 (1.1%)
		Vomiting	1 (1.1%)
		Constipation	1 (1.1%)
		Blood and Lymphatic System Disorders	4 (4.6%)
		Anemia	4 (4.6%)
		Nervous System Disorders	3 (3.4%)
		Insomnia	1 (1.1%)
		Headache	1 (1.1%)
		Dizziness	1 (1.1%)
		Hepatobiliary Disorders	2 (2.3%)
		Hepatic function abnormal	2 (2.3%)

System Organ Class/Preferred Term	Total (N = 67) 67 (77.0%)	
Number of Subjects with at Least One Event		
	Metabolism and Nutrition Disorders	7 (8.0%)
	Decreased Appetite	3 (3.4%)
	Hypertriglyceridaemia	2 (2.3%)
	Oedema Peripheral	1 (1.1%)
	Hyperglycaemia	1 (1.1%)
	Infections and Infestations	1 (1.1%)
	Conjunctivitis	1 (1.1%)
	Immune System Disorders	1 (1.1%)
	Anaphylaxis	1 (1.1%)

The incidence of Grade 3 or greater AEs was 10.3%, and the incidence of Grade 3 or greater treatment-related AEs was 2.3%. Grade 3 or greater AEs are shown in the table below:

Grade 3 or greater AEs in three phase I clinical studies of SHR-1210 in China (data as of 31 Oct., 2016)

System Organ Class/Preferred Term		Total (N = 67)	
Number of Subjects with at Least One Event		67 (77.0%)	
Highlighted are treatment-related AEs as judged by the investigator			
Investigations	5 (5.7%)	Gastrointestinal Disorders	2 (2.3%)
Hypochloraemia	2 (2.3%)	Abdominal Pain	1 (1.1%)
		Upper Gastrointestinal Haemorrhage	1 (1.1%)
Hyponatraemia	2 (2.3%)		

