8.2.3 Hepatic enzyme abnormalities

If the levels of AST and/or ALT are abnormal and meet the laboratory test abnormalities shown in the table below, such cases of hepatic enzyme abnormalities should be reported as SAEs. The investigator is required to strengthen the follow-up of the subjects, who should be followed up until their hepatic enzyme levels recover to the normal or baseline level.

Baseline Period	Normal (AST/ALT and TBIL)	Abnormal (AST/ALT/TBIL)
Treatment period	ALT or AST $\geq 3 \times \text{ULN}$ with TBIL $\geq 2 \times \text{ULN}$ and ALP $\leq 2 \times \text{ULN}$ and no hemolysis	AST or ALT $\geq 2 \times \text{baseline level}$, and $\geq 3 \times \text{ULN}$ or AST or ALT $\geq 8 \times \text{ULN}$ with increase in TBIL by $\geq 1 \times \text{ULN}$ or TBIL level $\geq 3 \times \text{ULN}$

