8.5 Adverse Events of Special Interest

When an AE of special interest specified in the study protocol occurs, the investigator must fill out the "Report of Adverse Event of Special Interest for Hengrui Clinical Studies" and report to the sponsor within 24 h of knowing the event. If an AE of special interest is also an SAE, the "NMPA Serious Adverse Event Report Form" must also be completed.

- Grade ≥ 3 infusion reaction
- Grade ≥ 2 diarrhea/colitis, uveitis, interstitial pneumonitis
- Other Grade ≥ 3 immune-related AEs

- Any possible events of hepatic enzyme abnormalities (see 8.2.3, lacking other related causes of the abnormalities at the same time, e.g., PD, acute viral hepatitis, cholestasis, concomitant medication, concurrent liver disease, etc.)
- Grade 4 amylase or lipase increased

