- Immune-related TEAEs (irAEs)

The incidence of an AE will be calculated based on the number of subjects experiencing the AE, instead of the number of AE episodes.

SIEs include:

- Grade ≥ 3 infusion reaction
- Grade ≥ 2 diarrhea/colitis, uveitis, and interstitial pneumonia
- Other Grade ≥ 3 irAEs
- Grade 4 amylase or lipase increased
- Reactive capillary endothelial proliferation
- Hepatic enzyme abnormal

Time to the first onset of event (days) = Date of first onset of event – Date of first dose + 1;

All AEs will be listed. Treatment-related AEs, SAEs, irAEs, and AEs leading to treatment discontinuation, interruption, or dose reduction will be listed separately.

In addition, AEs will be summarized by group (apatinib 250 mg + SHR1210 200 mg, apatinib 375 mg + SHR1210 200 mg) using descriptive statistics, including but not limited to the following:

- Any TEAE
- Treatment-related TEAE
- Any treatment-emergent serious adverse event (TESAE)
- Treatment-related TESAE
- CTCAE Grade ≥ 3 TEAE
- CTCAE Grade ≥ 3 treatment-related AEs
- Special interest events (SIEs)
- Immune-related adverse events (irAEs)
- Treatment-related AEs leading to treatment discontinuation
- Treatment-related AEs leading to discontinuation of SHR-1210
- Treatment-related AEs leading to discontinuation of apatinib
- Treatment-related AEs leading to interruption of SHR-1210
- Treatment-related AEs leading to interruption of apatinib
- Treatment-related AEs leading to dose reduction of apatinib

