Appendix 2: List of Preferred Terms for Special Interest Events

Special Interest Event	Classification	AE Preferred Term (coded as per v24.0)
Grade 4 amylase or lipase increased	Amylase increased	Amylase increased
Grade 4 amylase or lipase increased	Lipase increased	Lipase increased
Reactive capillary endothelial proliferation		Reactive capillary endothelial proliferation
Grade ≥ 3 infusion reaction		Infusion related reaction
Grade ≥ 2 diarrhea/colitis	Colitis	Colitis ulcerative
Grade ≥ 2 diarrhea/colitis	Colitis	Enterocolitis
Grade ≥ 2 diarrhea/colitis	Colitis	Colitis
Grade ≥ 2 diarrhea/colitis	Diarrhea	Frequent bowel movements
Grade ≥ 2 diarrhea/colitis	Diarrhea	Diarrhoea
Grade ≥ 2 uveitis		Uveitis
Grade ≥ 2 uveitis		Eye pain
Grade ≥ 2 interstitial pneumonia		Interstitial lung disease

Special Interest Event	Classification	AE Preferred Term (coded as per v24.0)
Hepatic enzyme abnormal		Hepatic enzyme abnormal
Other Grade ≥ 3 irAEs	Immune-mediated lung disease	Immune-mediated lung disease
Other Grade ≥ 3 irAEs	Pneumonia	Pneumonitis
Other Grade ≥ 3 irAEs	Immune-related hepatitis	Immune-mediated hepatitis
Other Grade ≥ 3 irAEs	Hepatic function abnormal	Hepatic function abnormal

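### SAP Appendix 2 does not implement the special-interest definitions: it misses Grade 2 events under two lung terms, and laboratory-defined liver events coded as enzyme or bilirubin increases

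*SAP*

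**What the plan says.** **Lung.** Protocol 8.5 lists "Grade ≥ 2 diarrhea/colitis, uveitis, interstitial pneumonitis" as events of special interest, followed by a residual class, "Other Grade ≥ 3 immune-related AEs". SAP 5.4.3 carries the same threshold: "Grade ≥ 2 diarrhea/colitis, uveitis, and interstitial pneumonia". Appendix 2 then assigns preferred terms. Its row "Grade ≥ 2 interstitial pneumonia" contains only *Interstitial lung disease*. Its residual Grade ≥ 3 class contains "Immune-mediated lung disease" and *Pneumonitis*.

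**Liver.** Protocol 8.5 includes "Any possible events of hepatic enzyme abnormalities (see 8.2.3, lacking other related causes of the abnormalities at the same time". Section 8.2.3 applies "If the levels of AST and/or ALT are abnormal and meet the laboratory test abnormalities shown in the table below" and makes such cases reportable as SAEs. SAP 5.4.3 keeps the hepatic category by name but does not repeat the laboratory criteria. Appendix 2 gives it one preferred term, *Hepatic enzyme abnormal*. *Immune-mediated hepatitis* and *Hepatic function abnormal* are listed under the residual Grade ≥ 3 class.

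**Eye.** Appendix 2 counts *Eye pain* from Grade 2 as uveitis and sets no condition on relatedness.

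SAP 5.4.3 refers to Appendix 2 for the specific classification. It tabulates special-interest events twice: by population or cohort, and by apatinib dose group (250 mg and 375 mg).

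**The concern.** A list of preferred terms is what the programmer runs. If it is narrower than the definition it serves, the table reports something other than what the protocol set out to monitor. Here the same lung event at Grade 2 is in or out depending on which synonym it was coded to. A liver event defined by laboratory values is in or out depending on the wording of the adverse event entry, not on the values.

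The lung cut-off matters because Protocol 8.7 and 9.1 already direct treatment and allow interruption of SHR-1210 for immune-related pneumonitis at Grade 2. The special-interest tables are a natural place to look for pneumonitis and liver injury with this combination, so their rows should match their stated definitions.

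**Working it through.** There is no sample-size or error-rate figure to reproduce. The check treats the 17 preferred terms of Appendix 2, each with its grade cut-off, as a filter and passes lung and liver terms through it.

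| Coded term | Appendix 2 class | Grade 2 | Grade 3 | Grade 4 |
|---|---|---|---|---|
| *Interstitial lung disease* | Grade ≥ 2 lung | in | in | in |
| *Pneumonitis* | residual Grade ≥ 3 | out | in | in |
| *Immune-mediated lung disease* | residual Grade ≥ 3 | out | in | in |
| *Hepatic enzyme abnormal* | hepatic, no cut-off | in | in | in |
| *Hepatic function abnormal* | residual Grade ≥ 3 | out | in | in |
| *Immune-mediated hepatitis* | residual Grade ≥ 3 | out | in | in |
| ALT, AST or blood bilirubin increased | not listed | out | out | out |

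**Lung.** SAP 5.4.3 counts the highest grade when an event recurs in a subject. The loss is therefore limited to subjects whose worst event under the two misfiled terms is Grade 2 and who have no other qualifying lung event. Let q2 be the proportion of such subjects and q3 the proportion with Grade ≥ 3 under those terms. The tables show q3; the Grade ≥ 2 threshold would give q2 + q3. The documents give neither rate. As an illustration on assumed rates only, with q3 = 2% and q2 between 1% and 3%, the tables would show 2% instead of 3% to 5%. Even the Grade ≥ 3 events would appear in the residual class, not in the lung row.

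**Liver.** For a subject with normal baseline, 8.2.3 requires ALT or AST ≥ 3 × ULN with TBIL ≥ 2 × ULN, ALP ≤ 2 × ULN and no hemolysis. None of these conditions is a preferred term or a CTCAE grade. SAP 5.4.4 offers shift tables by clinical significance, a plot of median liver values by visit, and listings. None of them searches the values against 8.2.3.

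**How liver findings have been coded.** The earlier SHR-1210 tables in Protocol 1.7.1 show "Alanine Aminotransferase Increased" in 7 subjects, AST increased in 7, blood bilirubin increased in 3 and hepatic function abnormal in 2. The printed percentages use 87 subjects as denominator: 7/87 = 8.0%, 3/87 = 3.4%, 2/87 = 2.3%. At Grade 3 or above the second table shows AST increased in 2, ALT increased in 1 and blood bilirubin increased in 1. Neither table has a row for *Hepatic enzyme abnormal*. The figures show which terms have been used for liver findings with this drug. They do not show that any of these cases met 8.2.3.

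**The case against.** The strongest defence of the lung rows is literal. Protocol 8.5 says interstitial pneumonitis, which could be a narrower entity than pneumonitis, and it provides a residual Grade ≥ 3 class for other immune-related events. On that reading the split is deliberate. It cannot be excluded, but neither document defines it, and Protocol 8.7 and 9.1 name no lung irAE other than immune-related pneumonitis. An intended split would have to be stated.

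Second, Appendix 2 may not filter all adverse events. Investigators complete a special-interest report form under Protocol 8.5, and the appendix might only classify what they report. The SAP does not say. The gap would remain: a reported Grade 2 *Pneumonitis*, or a liver event coded as ALT increased, would have no row to go into. The *Eye pain* point does depend on this, because under that reading the term may simply be how a reported uveitis was coded. It is minor.

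Third, a site that copies the protocol's hepatic wording may well produce the listed term. Coding follows MedDRA v24.0, which the documents do not reproduce, so the hepatic loss is conditional on how each event is coded.

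Fourth, the events are not lost to the report. They remain in the TEAE summaries and listings. Lung events judged immune-related enter the irAE summary, which has no grade cut-off. Events meeting 8.2.3 are SAEs and enter those summaries. All of this stands, and it limits the consequence.

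**Conclusion.** Appendix 2 does not deliver the special-interest definitions of Protocol 8.5 and SAP 5.4.3 in two places. Grade 2 events coded *Pneumonitis* or *Immune-mediated lung disease* are left out. Events meeting 8.2.3 enter the hepatic category only if coded *Hepatic enzyme abnormal*: under an ALT, AST or bilirubin term they enter at no grade, and under the two other hepatic terms only at Grade ≥ 3 in another class. The effect is confined to the two sets of special-interest tables, and its size in subjects cannot be derived.

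Some stronger readings are tempting but unsupported:

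- That all Grade 2 lung events disappear. Those coded *Interstitial lung disease* are kept.
- That Appendix 2 finds liver events through a single term. It has three hepatic terms; only the laboratory-defined category rests on one.
- That the Stage I primary endpoint is understated. That endpoint is overall AE and SAE incidence and severity, which Appendix 2 does not alter.
- That the phase I percentages measure the loss. They count coded terms, not cases meeting 8.2.3.
- That uveitis is overstated. This depends on how Appendix 2 is applied.

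The conclusion assumes that Appendix 2 as shown is complete and will be followed as written.

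**What to change.** In SAP Appendix 2 and 5.4.3:

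1. Move *Pneumonitis* and *Immune-mediated lung disease* to the Grade ≥ 2 lung row. If the sponsor means to keep the split, define and justify it in the SAP.
2. Identify hepatic special-interest events by flagging the collected ALT, AST, TBIL and AKP values against 8.2.3, in addition to the preferred term. The flag gives candidates only: 8.5 requires other causes to be absent, 8.2.3 requires no hemolysis for subjects with normal baseline, and the listed laboratory panels name no hemolysis test. Medical review or the special-interest report form should settle each flagged case.
3. Count *Eye pain* as uveitis only when the investigator reported it as a special-interest or immune-related event.
4. State whether Appendix 2 filters all TEAEs or classifies events that investigators reported as special-interest.

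The laboratory values are already collected, so the cost is an appendix edit, some reprogramming of the special-interest tables and medical review of flagged liver cases. The reported lung and liver special-interest incidence may become less favourable.
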